Patients who have undergone MRI perfusion imaging *without* referral for cardiac CTA will also be eligible for this study. For these patients, the coronary CT at rest will be performed as a research procedure followed by the stress portion of the CT perfusion study. No interpretation will be performed before the stress portion of the exam so all of these patients will receive the stress portion of the exam. These patients must have the clinically indicated MRI stress perfusion imaging as well as the research cardiac CTA with CT perfusion study completed within 60 days.

Patients who have undergone MRI stress perfusion imaging with a prior cardiac CTA will also be eligible for this study. These patients will only undergo the stress portion of CT perfusion study. These patients must have the clinically indicated cardiac CTA and SPECT as well as the research CT perfusion study completed within 60 days.

The CT perfusion scans will be analyzed and read by two highly trained CT readers (cardiologist and radiologist). In addition to assessing the safety and tolerability of the Lexiscan™ perfusion study, the CT perfusion findings will be compared diagnostically to SPECT and/or invasive catheter angiography if this is performed clinically after the research procedure.

Patient Flow Chart

Patients with heart rates > 65 bpm may receive beta-blockers in order to reduce their heart rate to values < 60 bpm. Patients with contraindications to the use of beta-blockers (chronic obstructive pulmonary disease, asthma sensitive to beta agonists, second- or third-degree heart block, hypotension as defined by systolic blood pressure <100 mmHg) are in principle eligible for participation in the study – however, no beta-blockers will be used in such individuals. Patients will receive nitroglycerin based on investigator judgment to better visualize the coronary arteries. Female subjects of childbearing potential will be given a urine pregnancy test prior to study enrollment. Pregnant persons will be excluded. Patients will receive a point-of-care serum creatinine test on the day of their research procedure before any contrast administration and patients with a serum creatinine greater than or equal to 1.5 mg/dL will be excluded from the study.

CT Coronary Angiography Protocol:

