A checklist will be made and each of the following events will be assessed by an investigator or designated personnel:

1. Hypotension (systolic BP < 90 or > 30 mm Hg decrease from baseline)
2. Hypertension (systolic BP > 200 mmHg)
3. Significant new heart block (type II 2nd degree or 3rd degree A-V block)
4. Bradycardia (heart rate < 45 bpm, sinus bradycardia or junctional rhythm)
5. Bronchospasm (requiring inhaler or other medical treatment)
6. Allergic reaction (hives, erythema, wheezing)

7. Chest pain
8. Nausea
9. Headache
10. Seizures

Additionally, a patient satisfaction questionnaire (detailed below) will be administered to all patients who undergo the CT perfusion scan following the research scan as well as a 30-day event rate (MACE defined by ED visit, hospitalization, ACS/MI, stroke, revascularization, significant new arrhythmia and death) will be assessed by chart review and follow-up phone call one month (+/- 3 days) from the scan.

Patient Satisfaction Survey:

Following the CT perfusion scan, the patient will be given a participant satisfaction survey. The purpose of this survey is to assess the patients' subjective experience with the different imaging modalities (CT vs. SPECT/MRI stress perfusion imaging). The seven question survey will assess: 1) the patient's perception of the overall ease or difficulty of the study, 2) length of the study, 3) perceived discomfort, 4) level of apprehension, 5) understanding of the nature of the test, 6) understanding of the results and 7) willingness to undergo the test again. Each question will have a quantitative score of 1 – 4. Patients who have not yet undergone SPECT imaging at the time will be asked the SPECT specific questions at the time of the 30-day follow-up if they have undergone the SPECT testing at that time. If not, the patient will not be asked the SPECT questionnaire.

D.2 STATISTICAL METHODS / SAMPLE SIZE JUSTIFICATION

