2. Subject must have been referred for cardiac CT angiography OR subject must have undergone clinically indicated SPECT OR subject must have undergone clinically indicated SPECT with prior cardiac CT angiography OR subject must have undergone a clinically indicated MRI stress perfusion imaging.
3. Subject must be 18 – 85 years of age.
4. Subject must provide written informed consent prior to any study-related procedures being performed.
5. Subject must be willing to comply with all clinical study procedures.

Exclusion Criteria:

The presence of the following excludes subjects from the study: (All answers must be “**NO**” for subject to be eligible.)

1. Subject is a pregnant or nursing female. Exclude the possibility of pregnancy:
 - By testing (serum or urine beta HCG) within 24 hours before study agent administration, or
 - By surgical sterilization, or
 - Post menopausal, with minimum one (1) year history without menses.
2. Subject has severe asthma or COPD requiring frequent inhaler use.
3. Subject has prior diagnosis of obstructive CAD that has not been revascularized.
4. Subject with implanted rhythm devices (pacemaker, defibrillator).
5. Subject has significant arrhythmia.
6. Subject has high grade heart block.
7. Subject has resting heart rate < 45 bpm, systolic blood pressure <90 mm Hg, or has consumed caffeine within the last 12 hours.
8. Subject has an acute psychiatric disorder.
9. Subject is unwilling to comply with the requirements of the protocol.
10. Subject has previously entered this study.
11. Subject has an allergy against iodinated contrast agents or pharmaceutical stressors used in this study.
12. Subject suffers from claustrophobia.
13. Subject has impaired renal function (creatinine > 1.5 mg/dl).
14. Subject is in unstable condition.
15. ST-elevations, new transient ST changes greater than 0.05mV or T- wave inversions with symptoms
16. Subject cannot safely be administered Lexiscan™ per prescribing information as determined by investigator
17. Subject has received interventional (PCI, stenting) or surgical (CABG) treatment that may alter the cardiac condition regarding myocardial perfusion status and/or stenosis degree between cardiac CTA, SPECT, MRI, and/or CT stress perfusion studies.

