Patients with heart rates >65 bpm may receive beta-blockers in order to lower the heart rate to values <60 bpm. Patients with contraindications to the use of beta-blockers (chronic obstructive pulmonary disease, asthma sensitive to beta agonists, second- or third-degree heart block, hypotension (<100 mm Hg systolic) are in principle eligible for participation in the study – however, no beta-blockers will be used in such individuals.

There will not be any eligibility criteria for any subpopulations. In addition, there will not be any targeted involvement of special classes of subjects, such as fetuses, neonates, pregnant women, children, prisoners, institutionalized individuals, or others who may be considered vulnerable populations. All race and ethnicities and both genders will be considered for inclusion into the study. Subjects under the age of 18 will not be considered for inclusion into this study. This research will only be conducted at the Medical University of South Carolina.

Targeted/Planned Enrollment Table

Total Planned Enrollment: 100

TARGETED/PLANNED ENROLLMENT: Number of Subjects			
Ethnic Category	Sex/Gender		
	Females	Males	Total
Hispanic or Latino	0	0	0
Not Hispanic or Latino	50	50	100
Ethnic Category: Total of All Subjects*	100		
Racial Categories			
American Indian/Alaska Native	0	0	0
Asian	0	0	0
Native Hawaiian or Other Pacific Islander	0	0	0
Black or African American	17	17	34
White	33	33	66
Racial Categories: Total of All Subjects*	50	50	100

E.1.b Sources of Materials

The research materials that will be obtained from living human subjects are: the cardiac SPECT, MRI stress perfusion, coronary catheterization, CT, and all applicable other imaging studies (e.g. echocardiography), progress notes, medication records, vital signs, medical history and demographics, and all other applicable clinical information.

The Principal Investigator, Sub-Investigator(s) and the Study Coordinator(s) will be the only personnel who will have access to subject identities, with the exception of any regulatory personnel (MUSC IRB auditors, etc.). All subject identities will be removed prior to publication.

E.1.c Potential Risks

Patient discomfort

The study prolongs the discomfort for the patient of lying supine by approximately 30 minutes for the CT study. Subjects may find it uncomfortable to lie still during the scans. A study duration of no more than 60 minutes room time will be used to minimize this discomfort.

Vein puncture

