Common side effects of the drug Nitroglycerine (a Nitrate available in 0.4 mg or 0.8 mg for sublingual (under the tongue) administration include headache which may be severe and persistent and may occur immediately after use. Vertigo, dizziness, weakness, palpitation (irregular beatings of the heart), and other symptoms of postural hypotension (low blood pressure) may develop occasionally, particularly in upright, motionless subjects. Fainting, which may lead to falls and injuries has also been reported. Flushing, drug rash, and flaky skin have been reported in subjects receiving nitrate therapy.

Use of Regadenoson

The following reactions are listed as warnings and precautions when using regadenoson (Lexiscan™, injected as a 0.4 mg bolus): myocardial ischemia, sinoatrial and atrioventricular nodal block, hypotension, and bronchoconstriction. The following adverse reactions associated with regadenoson are considered transient and are listed in the package insert: dyspnea or urge to breathe deeply, headache, flushing, chest discomfort, angina pectoris or ST segment depression, lightheadedness/dizziness, chest pain, nausea, abdominal discomfort, impaired taste, and feeling hot. Dyspnea can occur during stress myocardial perfusion imaging with associated arrhythmias such as hypoxia induced bundle branch block. The first signs of these rare side effects will cause the termination of the examination.

CT Examination performed with the new Force scanner

The Siemens SOMATOM™ Force is a new computed Tomography X-ray system, which is substantially equivalent to the previous systems (SOMATOM™ Definition and the SOMATOM™ Definition Flash). The SOMATOM™ Force scanner received 510(k) FDA-approval for clinical use on the 17th April 2014.

The SOMATOM™ Force scanner has been used for two other research studies with excellent results. The risks associated with this CT scanner are comparably low to other CT scanners.

Acquisition of patient information

The risks associated with gathering this information are believed to be very low. This information will be stored on a password-protected computer and network server and in a locked office (ART Cardiac Imaging Research Office). The data from this study will be accessible only to the team of researchers from this application.

E.2 ADEQUACY OF PROTECTION AGAINST RISKS

E.2.a Recruitment and Informed Consent

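### Third-degree heart block is eligible in principle in two places but barred by the high-grade-block exclusion, and the protocol never defines high grade

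*Combined protocol and SAP*

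**What the plan says.** Two paragraphs deal with heart-rate control before the scan, one in D.1 Research Design (after the patient flow chart) and one in E.1.a (after the exclusion criteria). Each lists conditions that rule out beta-blockers: COPD, certain asthma, heart block and low systolic pressure. Each then says what follows for eligibility.

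- D.1: patients with "second- or third-degree heart block, hypotension as defined by systolic blood pressure <100 mmHg) are in principle eligible for participation in the study".
- E.1.a: patients with "second- or third-degree heart block, hypotension (<100 mm Hg systolic) are in principle eligible for participation in the study".

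In both, the only stated consequence is that no beta-blocker is given.

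The E.1.a exclusion list is introduced by "The presence of the following excludes subjects from the study", and every answer must be no. Item 6 is "Subject has high grade heart block". The term high grade is defined neither there nor elsewhere.

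Two further places bear on the point. E.1.c, Use of Regadenoson, names among the drug's warnings and precautions "myocardial ischemia, sinoatrial and atrioventricular nodal block, hypotension, and bronchoconstriction". Item 3 of the checklist in D.1, Safety and Tolerability Assessment, is "Significant new heart block (type II 2nd degree or 3rd degree A-V block").

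**The concern.** The beta-blocker paragraphs do more than say when a beta-blocker is withheld. They also make a statement about study eligibility, and they name third-degree block. Someone screening from either paragraph would conclude that third-degree block does not keep a patient out. Someone screening from the numbered list would conclude that it does.

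Two things are at stake. The first is a clear eligibility rule in a study whose main stated purpose (D.2) is feasibility, safety and tolerability of an agent with a nodal-block warning. The second is one item of the safety checklist. It counts new block of type II second degree or third degree, and a patient who already has third-degree block cannot newly acquire it. The plan does not say whether such a patient would be recorded as event-free or as not assessable.

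**Working it through.** There is no figure to reproduce. The check sets each condition in the beta-blocker parenthesis against the exclusion that limits it, and asks whether both statements can hold.

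| Condition named as eligible in principle (D.1, E.1.a) | Limiting exclusion (E.1.a) | Can both hold? |
|---|---|---|
| COPD or asthma | Item 2: severe disease with frequent inhaler use | Yes: milder disease is eligible |
| Systolic pressure below 100 mm Hg | Item 7: below 90 mm Hg | Yes: 90 to 99 mm Hg is eligible |
| Second-degree block | Item 6: high grade block | Undetermined: depends on the missing definition |
| Third-degree block | Item 6: high grade block | No, on any ordinary reading of high grade |

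1. **A severity gradient reconciles the first two rows.** The eligible group is the milder part of the condition and the excluded group is the more severe part.
2. **The same reasoning fails for third-degree block.** The most severe form is itself named as eligible, so no milder remainder is left for the sentence to describe.
3. **Paced patients do not explain it.** Exclusion 4 bars implanted pacemakers and defibrillators, so the sentence cannot be meant for patients whose block is already paced.
4. **Second-degree block stays open.** The only grading of block in the documents is the safety checklist, which puts type II second-degree with third-degree as significant. If exclusion 6 followed that grouping, type II would be in conflict and type I would not. But the checklist grades a safety event and does not define the exclusion term, so this cannot be settled from the text.
5. **Consequence for the checklist.** EKGs before and after dosing (D.1, Pharmaceutical Stress Protocol; E.2.b) can separate existing block from new block. Type I second-degree block could still be followed for progression. Pre-existing third-degree block could not, since it is already at the top of the checklist's definition.

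**The case against.** The best defence is that the paragraphs are about heart-rate control. On that view, eligible in principle means only that a contraindication to beta-blockers does not exclude by itself, and the numbered list, where any one item excludes, remains the operative rule. COPD, asthma and blood pressure already work that way. This is a fair reading and probably what was intended. But neither paragraph says it is subject to the list, the E.1.a version follows the list and can be taken as qualifying it, and this reading gives no reason to name third-degree block at all.

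The second defence is that other checks would stop such a patient:

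- E.1.a and E.2.a restrict entry to patients with non-specific ECG findings, and call for contraindications to be ruled out with the responsible physician.
- Exclusions 5 (arrhythmia) and 7 (resting heart rate below 45 bpm) may apply. Exclusion 16 turns on whether the agent can be given safely "per prescribing information as determined by investigator".
- A cardiologist reviews the EKG and history before the agent is given (D.1, E.2.b).
- A named investigator confirms eligibility in each case (E.5).

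This largely stands. A reader might infer from the contradiction that patients with complete heart block are likely to receive the stress agent. The documents do not support that, since several separate checks would have to fail. What the checks leave open is which eligibility rule is in force. Some of them operate after consent, and E.5 says site records will not be formally monitored, so a wrong classification could go unnoticed.

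**Conclusion.** The contradiction is real and certain for third-degree block. It rests on one assumption: that third-degree block counts as high grade, which is the ordinary meaning and fits the checklist's grouping, though the protocol does not say so. For second-degree block the finding is a missing definition.

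Two other stronger readings are tempting and should not be drawn. One is that the protocol contradicts itself for second-degree block as a whole. Type I need not conflict, and type II conflicts only if the checklist's grading is borrowed for exclusion 6. The other is that a primary safety outcome is compromised to a measurable extent. New heart block is one of ten checklist items, none designated primary, and the documents give no frequency of heart block from which to size an effect.

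The number of patients affected is probably small but cannot be stated. No sample size, comparison or estimate in D.2 changes. The matter should still be corrected, because two stated rules give opposite answers for the same patient in a study of an agent with a nodal-block warning.

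**What to change.** The sponsor should reconcile the beta-blocker paragraphs in D.1 and E.1.a with exclusion 6, so that all three give the same answer for each degree of heart block, and should state which degrees count as high grade. One way to draft this is to make the eligible-in-principle sentence expressly subject to the numbered exclusions in both places. Which patients may enter is a clinical decision for the sponsor, and this review takes no position on it.

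If the reconciled text admits any patient whose baseline block already meets the checklist definition, the safety section should say how item 3 is scored for that patient.

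The cost is one clause in two paragraphs and a short definition. Sample size, procedures and analysis are unaffected.

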Studies will be performed using a 3rd generation, dual source CT scanner capable of coronary imaging at < 1mSv (Siemens, SOMATOM™ Force). The coronary CTA will be performed based on standard clinical indications that conform to published appropriate use criteria. The scan will be done using our usual clinical protocol with administration of 30 – 60 cc of an intravenous contrast agent (Ultravist 370). Acquisition mode (axial, prospective, retrospective or flash) is chosen based on heart rate, rhythm and body size. We will accept patients who have the SPECT study done within 30 days of the scheduled CTA and/or research scan(s).

Pharmaceutical Stress Protocol:

Pharmacological stress testing will be performed with a single injection of 0.4 mg of regadenoson (Lexiscan™) under physician and nursing supervision per MUSC clinical protocol. The cardiologist responsible for clinical stress administration will review a pre-Lexiscan™ EKG and patient medical history to ensure Lexiscan™ can be administered safely. A post-Lexiscan™ EKG will be obtained and read and the cardiologist will determine if and when the patient can be discharged safely.

Analysis of CT Coronary Angiography Images:

CT coronary angiograms will be evaluated by consensus of two experienced investigators. Images will be analyzed using both axial source images and by analyzing dedicated 2D and 3D visualization techniques such as Maximum Intensity Projection (MIP), curved Multiplanar Reconstruction (MPR) and 3D Volume Rendering (VRT).

CT myocardial perfusion protocols:

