Patients will undergo dynamic, first pass, stress perfusion imaging during maximal hyperemia induced with Lexiscan™. Imaging will commence approximately 90 seconds after a bolus of Lexiscan™ (0.4 mg per each 5 mL injection). The Lexiscan™ is followed immediately by a bolus of 10 cc saline. In order to achieve the correct timing of the dynamic image acquisition, contrast administration will begin approximately 80 seconds after the Lexiscan™ bolus to allow the contrast to reach the heart at the moment of maximal hyperemia. Data will be acquired for 30 seconds with both X-ray tubes set at 80 – 100 kV, a gantry rotation time of 0.28 seconds, and a tube current of 300 mAs per rotation. Temporal resolution is approximately 75 ms. Patients will be instructed to hold their breath for the first 15 seconds of the scan, as this is the most important portion of the data acquisition for quantifying myocardial blood flow. They will then be instructed to breath shallowly for the remaining 15 seconds. Perfusion imaging is performed in an ECG-triggered shuttle mode in which the table shifts between two z-positions of the heart to allow coverage of nearly the entire left ventricle. End systolic imaging is used to reduce motion artifacts, to image the heart at its smallest dimensions, and to reduce beam-hardening artifacts from contrast in the LV cavity. The relatively fast rotation time combined with the dual source system gives markedly improved temporal resolution, which helps to reduce motion artifacts associated with the rise in heart rate that frequently occurs after Lexiscan™ administration. With a detector width of 38 mm and 10% overlap between the two imaging positions, the coverage of the acquisition is 73 mm. In some patients, small portions of the base or apex could be cut off. A total of 14 or 15 image volumes during myocardial passage of the contrast bolus will be acquired. CT MPI studies will use 40 – 50 mL of contrast agent (Ultravist 370) administered at a flow rate of 4 – 6 mL/s. Following the perfusion imaging, the Lexiscan™ will be

reversed with 1 mg/kg of aminophylline per standard clinical protocol if indicated by the supervising physician.

CT Perfusion Data Reconstruction and Analysis:

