Dynamic CT MPI data are reconstructed with a section thickness of 3 mm and a 2 mm increment with a medium smooth convoluted kernel (B30). The data are processed with the volume perfusion CT body application software and workstation (Siemens). After motion correction and 4D noise reduction, a double arterial input function is defined by placement of ROIs in the descending aorta in the cranial and caudal regions of the covered volume. After a volume of interest is manually defined around the left ventricle, the left ventricular myocardium is automatically segmented. A dedicated parametric deconvolution algorithm based on a two-compartment model of intravascular and extravascular space is used to derive myocardial blood flow and the volume transfer constant (k^{trans}) from the time-attenuation curves for each voxel.²³

Quantitative Measures of Myocardial Blood Flow from CT:

CT perfusion images will be analyzed on a dedicated console using commercially available software (Syngo Volume Perfusion™) as previously described.²⁴ Evidence of ischemia will be determined initially by visual comparison of rest and stress CT perfusion scans. Perfusion defects will be visually rated as reversible (only present at stress), fixed (present at both rest and stress) and mixed (more pronounced at stress, partly reversible at rest). Quantitative analysis of myocardial perfusion will be performed and mean blood volume (MBV), mean blood flow (MBF), and mean transit time (MTT) of each myocardial segment will be recorded. Readers will be blinded to the results of SPECT or invasive angiography examinations. The values obtained will be compared to historical published values for each parameter (MBF, MBV, and MTT) obtained using older generation CT perfusion protocols, MRI perfusion, or dynamic perfusion scanning.

Analysis of SPECT images:

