This study is intended to primarily demonstrate feasibility, safety, and tolerability of Lexiscan™ for use as a coronary vasodilator during perfusion CT imaging. The study is not powered to prove the diagnostic accuracy of perfusion CT imaging with low radiation compared to SPECT or the current gold standard approach of invasive coronary angiography with invasive fractional flow reserve (FFR) measurement. Nonetheless, we will use the available comparative data for each technique (SPECT, MRI stress perfusion imaging, and invasive angiography) to help design subsequent clinical trials that are adequately powered for an accuracy endpoint. We anticipate that about 15 out of the 30 participants who undergo the CT perfusion portion of the study will have available cath comparisons.

Continuous data are displayed as mean ± SD, if normally distributed, or median and interquartile range if not normally distributed. Binary data are are displayed as proportions. Data will be reported as means ± SD or rates with 95 percent confidence intervals. A difference with P value of 0.05 or less will be considered significant.

Subjective image quality scores will be compared using the Chi-squared test with the Yates continuity correction for categorical variables and inter-observer agreement for image quality will be calculated using Cohen kappa (K) statistics and interpreted as follows: ≤ 0.20 slight or poor agreement, 0.20 – 0.40 fair agreement, 0.40 – 0.80 moderate agreement, ≥ 0.80 excellent agreement. For each group, comparisons of patient characteristics will be performed using the Chi-squared test for categorical variables and t-test or Mann-Whitney-U-test for continuous variables as appropriate.

Quantitative data (CNR, radiation dose) will be tested using a non-parametric significance test.

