We will present comparisons of normal or abnormal perfusion determined from SPECT/MRI stress perfusion imaging or CT perfusion using the standard 17-segment model. We will also present a comparison of ischemia by CT perfusion (based on vascular territory) compared to anatomic evidence of significant CAD at catheterization. Any segments cut off by the limited z-axis scan range on perfusion CT will be excluded. Given 30 patients, we will have a maximum of 510 regions available to compare CT perfusion and SPECT/MRI stress perfusion. We will first perform a binary analysis where each segment is classified as either normal or abnormal, since the relative severity of perfusion defects has not been defined for CT. If feasible based on the number of patients with SPECT/MRI stress perfusion scans, we will compare the number of abnormal segments in each patient by each methodology using a kappa statistic. We will also use standard SPECT/MRI stress perfusion grading of perfusion (1 – 4 scale) and a similar scale for CT perfusion defect severity (also 1 – 4) based on prior measurements of absolute myocardial perfusion (ml/100 ml/min) with each segment graded as 1, 2, 3 or > 4 standard deviations from the norm. We will then perform linear regression (Pearson's correlation) to derive R values for CT perfusion versus SPECT/MRI stress perfusion imaging perfusion grade for each segment.

E. PROTECTION OF HUMAN SUBJECTS

E.1 RISK TO THE SUBJECTS

E.1.a Human Subject Involvement and Characteristics

This study will include 100 adults who present to the MUSC ED, hospital, or outpatient clinic with a clinical history and symptoms suspicious for cardiac ischemia and who have undergone or will likely undergo nuclear stress testing (SPECT).

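### Of the four regadenoson warnings, only myocardial ischemia has no objective or treatment-based item on the scan-day safety checklist, although the EKGs that could supply one are already read

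*Combined protocol and SAP*

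**What the plan says.** Section D.2 states the purpose: "This study is intended to primarily demonstrate feasibility, safety, and tolerability of Lexiscan™". It also commits to a reporting format: "Data will be reported as means ± SD or rates with 95 percent confidence intervals".

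Two EKGs bracket the drug. Section D.1 (Pharmaceutical Stress Protocol) has the cardiologist review one beforehand to clear dosing, and then: "A post-Lexiscan™ EKG will be obtained and read and the cardiologist will determine if and when the patient can be discharged safely". Section E.2.b repeats both readings. Neither section gives the time of the second tracing after the bolus. Under the D.1 perfusion protocol, Lexiscan may be "reversed with 1 mg/kg of aminophylline per standard clinical protocol if indicated by the supervising physician".

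Section D.1 (Safety and Tolerability Assessment) sets a checklist of ten events: hypotension, hypertension, significant new heart block, bradycardia, bronchospasm, allergic reaction, chest pain, nausea, headache and seizures. Follow-up adds a 30-day outcome, "MACE defined by ED visit, hospitalization, ACS/MI, stroke, revascularization, significant new arrhythmia and death", collected by chart review and a phone call at one month.

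Elsewhere in the plan ischemia is an imaging finding. Section D.1 (Quantitative Measures) says "Evidence of ischemia will be determined initially by visual comparison of rest and stress CT perfusion scans", and D.2 adds "We will first perform a binary analysis where each segment is classified as either normal or abnormal".

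Section E.1.c (Use of Regadenoson) names four warnings: myocardial ischemia, nodal block (sinoatrial and atrioventricular), hypotension and bronchoconstriction. It also lists ST segment depression among the transient reactions in the package insert.

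**The concern.** The checklist follows the drug's warnings closely, except for ischemia. That event has only a symptom, although its EKG sign is on a tracing that the study already obtains and has read.

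Two things are lost from the safety results if the checklist is used as written. A patient with ST change and no pain is not counted. A patient with chest pain is counted, but the report cannot say whether the EKG changed. The second matters because chest pain is the example presenting symptom in inclusion criterion 1, so by itself it is a weak marker of an event related to the test. Ischemia under stress is also plausible here: in the clinical-CTA route, patients receive Lexiscan because the CTA showed a moderate, indeterminate or significant stenosis (D.1, Research Design).

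**Working it through.** The plan has no figure of its own to reproduce on this point. The main check is a side-by-side reading.

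**Step 1. Match the E.1.c warnings to the D.1 checklist.**

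| Warning in E.1.c | Checklist item | Type of criterion |
|---|---|---|
| Nodal block | 3 (heart block), 4 (bradycardia) | EKG grade of block; rate below 45 bpm |
| Hypotension | 1 | Systolic BP below 90, or a fall of more than 30 mm Hg |
| Bronchoconstriction | 5 (bronchospasm) | Needs an inhaler or other treatment |
| Myocardial ischemia | 7 (chest pain) | Symptom only |

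Three of the four have an objective or treatment-based item. Of the ten items, none records ST change.

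**Step 2. Look for another planned count.**
- MACE includes ACS/MI, so a scan-day infarction or ACS would be counted. Transient ST change without a clinical event would not.
- D.2 plans no analysis of EKG findings.
- The perfusion reading yields ischemia as a diagnostic result by segment, not as a safety event.

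**Step 3. What a rate would look like.** D.2 anticipates catheterization comparisons for "about 15 out of the 30 participants who undergo the CT perfusion portion of the study", so the planning figure for dosed patients is n = 30. The exact (Clopper-Pearson) 95% interval for x events in n has lower limit Beta(0.025; x, n − x + 1), or 0 when x = 0, and upper limit Beta(0.975; x + 1, n − x). For x = 0 the upper limit reduces to 1 − 0.025^(1/n).

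- 0/30: 1 − 0.025^(1/30) = 0.1157, so 0 to 11.6%
- 1/30: 0.1 to 17.2%
- 3/30: 2.1 to 26.5%
- 0/100, if all 100 enrolled were dosed: 1 − 0.025^(1/100) = 0.0362, so 0 to 3.6%

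These widths would apply to any event at these sample sizes. They show how precise the added line would be, not the effect of leaving it out. They also refer only to ST change present on the post-scan tracing. The tracing time is not given and aminophylline may come first, so they do not bound ST change at any time after dosing.

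**The case against.** The best case for leaving the plan alone has four parts.

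*Care and serious events are covered.* The cardiologist reads both tracings and decides discharge. E.1.c ends the examination at the first signs of the rare reactions, E.2.b provides monitoring, unanticipated problems go to the IRB (E.5), and ACS/MI is in MACE. All of this stands. A reader might infer that patients are unprotected or that ischemia is recorded nowhere; the documents do not support either. What these routes lack is a planned rate of ST change.

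*The item is hard to interpret.* Provoking ischemia is what a stress test does, there is no comparator, and a single tracing may miss a transient change. This stands too, and it limits what the result may be said to show. It does not remove the gap, since chest pain has the same ambiguity and is on the list.

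*The choice of ST change is a preference.* Flushing, dizziness and dyspnea are in E.1.c and also off the checklist. This is answered by the table: the proposal is not to list every known reaction, but to complete the protocol's own four warnings.

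*The data may be captured already.* The case report form and the institution's clinical stress protocol are not part of the documents, and E.1.b allows collection of other relevant clinical information. That is possible. Availability is still not a definition, and a threshold chosen after the tracings have been seen is weaker than one fixed beforehand.

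**Conclusion.** The point holds as a reporting improvement on a primary aim, at low cost. It is not an error: no planned analysis is invalid and no safeguard is missing. What is absent from the planned safety results is painless ST change on the post-scan EKG, together with any division of chest pain by EKG change.

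This assumes that the enumerated checklist is used as written and nothing further is recorded on the case report form. The intervals assume 30 dosed patients; the SPECT and MRI routes could make the number different, and 100 is the ceiling.

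Two stronger readings should be resisted. One is that a definite number of events will be missed. The documents give no rate of ST change and no share of changes that would still show on the tracing, so no count can be derived. The other is that zero events on the new item would show that ST change did not occur after dosing. It would show only that none was present when the tracing was taken.

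**What to change.** Add one item to the D.1 checklist: *New ischemic ST change, post- versus pre-Lexiscan EKG* (yes / no / unreadable). Write a single threshold into the protocol, to be applied by whichever cardiologist reads the tracings, since D.1 and E.2.b name a role that more than one person may fill. The 0.05 mV figure in exclusion criterion 15 is a possible starting point, used regardless of symptoms. It was set as an entry screen, however, and may be noisy in patients enrolled with non-specific ECG findings. Record the tracing time after the bolus and whether aminophylline was given first.

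In D.2, report the proportion among dosed patients with an exact 95% interval, cross-tabulated with chest pain, and state how many tracings were missing or unreadable. D.2 promises 95% intervals for rates without naming a method. The exact one is preferable because the usual normal-approximation interval collapses to a single point at zero events.

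Label the result *ST change present on the post-scan EKG*. State that it may miss transient change and does not separate drug harm from a positive stress response. No separate rhythm or conduction item is needed, since items 3 and 4 cover those.

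The cost is one field, two short notes and a short descriptive analysis, from EKGs already obtained and read. There is no new procedure and no change in sample size. The downside is one more imprecise event rate, open to misreading as drug harm or as reassurance unless the caveats are printed with it.
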